5.3 APPENDIX 3 DEMOGRAPHICS AND BASELINE CHARACTERISTICS, PRIOR OR CONCOMITANT MEDICATIONS

Demographics, baseline characteristics, medical surgical history

The following demographics and baseline characteristics, and medical and surgical history will be summarized using descriptive statistics on the mITT and FAS populations.

Demographic and baseline characteristics:

- age at screening visit in years as quantitative variable and in classes (<65, \geq 65 years, and (<75, \geq 75 years)
- gender (Male, Female)
- race (American Indian or Alaska Native, Asian, Black or African American, Native Hawaiian or Other Pacific Islander, White, Not Reported, Unknown)
- ethnicity (Hispanic or Latino, not Hispanic or Latino, Not Reported, Unknown)

Baseline (see definition in [Section 3.1](#)) safety and efficacy parameters (apart from those listed above) will be presented along with the safety and efficacy summaries.

Medical (or surgical) history includes general medical history and iTTP-specific medical history. Medical and surgical history will be coded to a LLT, PT, HLT, HLGT, and associated primary SOC using the MedDRA version currently in effect at Sanofi at the time of database lock.

iTTP-specific medical history includes the description of the previous episodes (initial and recurrent), the number of previous episodes, time since iTTP diagnosis defined by date of

iTTP-specific medical history – date of iTTP diagnosis + 1 day (in year) and if the participant was previously exposed to caplacizumab. This includes also the following characteristics assessed at baseline: ADAMTS13 activity (in quantitative and by class: <10/≥10%), platelet count (in quantitative only), LDH, cTnI, and serum creatinine (for these 3 last parameters: in quantitative and by class: ≤ULN/>ULN), and also Glasgow Coma scale assessment.

Prior or concomitant medications

All medications will be coded using the World Health Organization-Drug Dictionary (WHO-DD) using the version currently in effect at Sanofi at the time of database lock.

- Prior medications are those the participant used prior to first study IMP intake. Prior medications can be discontinued before first administration or can be ongoing during treatment period.
- Concomitant medications are any interventions received by the participant concomitantly to the study IMP during the TE period, ie, up to the last IMP administration + 28 days.
- Post-treatment medications are those the participant took in the period running from the end of the concomitant medications period up to the end of the study.

A given medication can be classified as a prior medication and/or as a concomitant medication and/or as post-treatment medication. If it cannot be determined whether a given medication was taken prior or concomitantly or post, it will be considered as prior, concomitant, and post-treatment medication.

The prior and concomitant and post-treatment medications will be summarized for the mITT population by anatomic and therapeutic level. The summaries will be sorted by decreasing frequency of Anatomical Therapeutic Chemical (ATC) category. In case of equal frequency, alphabetical order will be used. Participants will be counted once in each ATC category (anatomic or therapeutic) linked to the medication. Corticosteroids and anti-CD20 antibody treatments will be described through summaries.

In addition, all TPE will be described using the following variables: number (%) of participants requiring TPE, reason, time since first caplacizumab administration defined by date of TPE – date of first administration of caplacizumab (whatever marketed or study IMP) + 1 day (days), plasma product name, donor specification, plasma exchange technique, amount of plasma exchanged, multiple of plasma volume to be exchanged, and number of sessions for the desired plasma volume.

5.4 APPENDIX 4 DATA HANDLING CONVENTIONS

Analysis windows for timepoints

For efficacy endpoints, the actual times since first caplacizumab administration will be used, and for by-visit analyses of safety variables only scheduled visits will be used. PCSA analyses include all scheduled or unscheduled or additional visits assessments.

For PROs (during the Treatment Period) and PD parameters, the analysis visit windows are defined in [Table 7](#):

Table 7 - Analyses window definition

Scheduled visit post baseline	Target Study Day
Day 1	1
Week 1 (Day 2)	2
Week 1 (Day 3)	3
Week 2 (Day 8)	8
Week 3 (Day 15 – Day 21)	15
Week 4 (Day 22 – Day 28)	22
Week 5 (Day 29 – Day 35)	29
Week 6 (Day 36 – Day 42)	36
Week 7 (Day 43 – Day 49)	43
Week 8 (Day 50 – Day 56)	50
Week 9 (Day 57 – Day 63)	57
Week 10 (Day 64 – Day 70)	64
Week 11 (Day 71 – Day 77)	71
Week 12 (Day 78 – Day 84)	78
EOT (Week 13 (Day 85))	85
FU 7 days after EOT	7 PT
Additional FU Visit 1 (14 days after EOT)	14 PT
Additional FU Visit 2 (21 days after EOT)	21 PT
FU visit 28 days after EOT	28 PT
FU visit (EOS) 12 weeks after EOT	

Study days are calculated considering Day 1 as the day of first administration of study IMP for visit on-treatment and considering Day 1 as the day after the last administration of intervention for visit after treatment.

FU=Follow-up; EOT=End of treatment ; PT=Post-treatment

Additional assessments and hospitalization visits

All additional assessments and hospitalization visit measurements of laboratory data, vital signs and ECG will not be included in by-visit analyses. PCSA analyses include all scheduled or unscheduled or additional visits assessments.

Cumulative dose for caplacizumab

In case of missing doses, the minimum cumulative dose calculated from available values will be presented.

Handling missing data

Particular considerations for Platelet, LDH, cTnI, creatinine, ADAMTS13 activity, and anti-ADAMTS13 antibody parameters:

- When used for the efficacy derived endpoints, only **CENTRAL** data will be used. One of the exceptions will be the following:
 - In case of missing CENTRAL record for platelet, LDH, cTnI and creatinine (reported as “NOT DONE” in the rawdata) and a reason given, the missing record will be replaced according the following rule (in this order):
 - If a local record is available with matching sample date and time, the local result will be used to impute central value
 - If only 1 local result is available with same date, the local result will be used to impute central value
 - If multiple local records are available:
 - If central and local records have date and time, the local record with the closest sample time to the missing central record will be used
 - If central record has only sample date and not sample time, the **median** value from the local samples on the same date will be used to impute the missing central record.
 - If duplicates of central records with same date, time and results, only one record will be kept
 - If for the same date and time, one record is “NOT DONE” and one record has a result, the record with the result will be kept
 - In case of missing CENTRAL record for platelet, LDH, cTnI and creatinine (reported as “NOT PERFORMED” in the rawdata), the missing record will be replaced according the following rule (in this order):
 - If a local record is available with matching sample visit, the local result will be used to impute central value
 - If multiple local records are available:
 - the **median** value from the local samples on the same visit will be used to impute the missing central record.
 - If multiple central records are available for the same date, the median value from the central values will be used.
 - For ADAMTS13 activity if a central sample was not done, then a local value, if available, can be substituted for the particular missing value.
 - For antibody titers, only central assessments will be used.

Then, and only after the potential above imputations, to derive the efficacy derived endpoints concerning platelet, LDH, cTnI and creatinine parameters (like Remission, Clinical response, Refractory to therapy, Clinical Relapse, Clinical exacerbation, Time to ...), only 1 unique value per day will be retained; this one will correspond to the median value observed among all values recorded on the following time windows:

- [0-24h] according to the actual elapsed time from first dose (1st administration of caplacizumab, whether is the marketed caplacizumab as first dose within 4 hours prior to enrollment or first dose of IMP, and whether the first dose is intravenous or subcutaneous administration, ie, ignoring route of administration for calculation of actual elapsed time from first dose)
- [>24-48h]
- [>48-72h]
- And for the following days >3, by calendar day.
- The values resulting from these derivations will be the values used for the graphical representation of platelet, LDH and ADAMTS13 activity from Day 4.

Consecutive laboratory assessments are considered as 'consecutive visits' for efficacy endpoints.

A participant could potentially have missing laboratory assessment data, however, remission could still be confirmed at a subsequent laboratory value. In the case there is inadequate information to determine the remission status of a participant by the end of the study, the participant will be treated as not having achieved remission.

Clinical evidence of new or progressive ischemic organ injury

Clinical evidence of new or progressive ischemic organ injury is defined as any presence of following clinically significant iTTP event:

- Neurological event
- Elevated cardiac troponins
- Acute myocardial infarction
- Conduction abnormality
- Repolarization abnormality
- Heart failure
- Clinically significant renal event

which will be identified from the checkboxes in the "Clinically Significant TTP Event" eCRF form.

Exacerbation of TTP, Relapse of TTP and Other event will not be considered as clinical evidence of new or progressive ischemic organ injury.

Sustained Clinical Response

Sustained Clinical response is defined by the concomitance of the 3 following criteria for at least 2 consecutive visits (starting from D2):

- platelet count $\geq 150 \times 10^9/L$
- LDH $< 1.5 \times ULN$
- no clinical evidence of new or progressive ischemic organ injury

Remission

Remission is defined as (1) a sustained Clinical response (see above) associated with (2) Clinical remission or (3) Complete ADAMTS13 Remission, whichever occurs first, and defined as:

- Clinical remission: No TPE (*Plasma Exchange* form) and no anti-VWF therapy (Caplacizumab treatment) for ≥ 30 days (from the date that Clinical Response is achieved).
- Complete ADAMTS13 Remission: The attainment of ADAMTS13 activity level $\geq 50\%$ for at least 2 consecutive visits (starting from D2).

Time to event

For each of below time to event, in case of no observation of the event or death, the censoring date will be defined as the last non-missing value of the analyzed parameter (platelet count, LDH....) if any, else as the start date of treatment (defined as first caplacizumab administration [whatever marketed or study IMP]).

- Time to platelet count response will be calculated as follow:

Date of initial day of 2 consecutive days where platelet count $\geq 150 \times 10^9/L$ - Date of start of treatment

- Time to LDH $\leq 1 \times$ ULN will be calculated as follow:
Date where LDH $\leq 1 \times$ ULN for the first time - Date of start of treatment
- Time to serum creatine $\leq 1 \times$ ULN will be calculated as follow:
Date where serum creatine $\leq 1 \times$ ULN for the first time - Date of start of treatment
- Time to cardiac troponin I $\leq 1 \times$ ULN will be calculated as follow:
Date where serum creatine $\leq 1 \times$ ULN for the first time - Date of start of treatment
- Time to ADAMTS13 partial remission (ADAMTS13 activity between 20% [included] and lower limit of normal [LLN] [excluded]) at 2 consecutive visits after clinical response will be calculated as follow:
Date of initial day of 2 consecutive visits after clinical response with ADAMTS13 partial remission - Date of start of treatment
- Time to normalization of ADAMTS13 level defined as sustained ADAMTS13 level of $\geq 50\%$ at 2 consecutive visits after clinical response will be calculated as follow:
Date of initial day of 2 consecutive visits after clinical response with normalization of ADAMTS13 level - Date of start of treatment
- Time to reduction of anti-ADAMTS13 antibodies below the threshold of positivity (12 U/mL) will be calculated as follow:
Date of reduction of anti-ADAMTS13 antibodies below the threshold of positivity - Date of start of treatment

Refractory to therapy

Refractory to the therapy during the on-treatment period is defined as following:

- Lack of platelet count increment (over 2 consecutive days),
OR
- platelet counts $<50 \times 10^9/\text{L}$ AND LDH $>1.5 \times \text{ULN}$ despite 5 days of treatment.

Note: if the 2 consecutive values of platelet are the same, the condition is not met for refractory. Additionally, a patient can become refractory after a sustained platelet count response if he still is on therapy.

iTTP-related death during the on-treatment period and during the overall study period

The iTTP-related deaths will be derived from the ***Clinically Significant iTTP Event*** form with the ***Outcome*** field filled as Fatal.

Clinical Exacerbation

Clinical exacerbation is defined between a Clinical Response and a Clinical Remission as:

- platelet count decreases to $<150 \times 10^9/\text{L}$ (note that it is assumed that other causes of thrombocytopenia are excluded from the data collected in the database),
- with or without clinical evidence of new or progressive ischemic organ injury, within 30 days of stopping TPE or anti-vWF therapy.

Clinical Relapse:

Clinical relapse is defined after a Clinical Remission as:

- platelet count decreases to $<150 \times 10^9/\text{L}$ (with other causes of thrombocytopenia excluded)
- with or without clinical evidence of new ischemic organ injury
- confirmed by documentation of severe ADAMTS13 deficiency ($<10\%$)

Number of hospitalization (including hospital and ICU) days during the on-treatment period and during the overall study period

$$\sum_{1}^{x} (\text{Date of Discharge for hospitalization } X - \text{Date of Admission for hospitalization } X + 1)$$

Number of days in ICU during the on-treatment period and during the overall study period

$$\sum_{1}^{x} (\text{Date of Discharge in ICU } X - \text{Date of Admission in ICU } X + 1)$$

Number of TPE days (if participants started TPE) during the on-treatment and during the overall study period

Number of TPE days will be equal to the number of TPE occurrences/observations in the database during the respective periods.

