2.2 BACKGROUND

Immune-mediated thrombotic thrombocytopenic purpura (also known as aTTP) is a life-threatening, thrombotic microangiopathy characterized by severe thrombocytopenia, microangiopathic hemolytic anemia, and organ ischemia. It is an ultra-orphan disease with an annual incidence reported to be about 3 cases per million people in the US (6, 7).

It is caused by inhibitory autoantibodies to vWF-cleaving enzyme ADAMTS13 that result in a severe deficiency in the activity level of the enzyme. Severe deficiency (<10%) of ADAMTS13 enzyme activity has been recognized as a biomarker specific for iTTP and is used in the acute and long-term management of patients with iTTP (8).

Von Willebrand factor, a key protein in hemostasis, plays a pivotal role in the recruitment of platelets to sites of vascular injury. More than 90% of circulating vWF is expressed by endothelial cells and secreted into the systemic circulation as ultra-large vWF (ULvWF) multimers. Under high shear stress conditions such as in arterioles and capillaries, the platelet-binding A1 domain of the ULvWF multimers interact spontaneously with the glycoprotein Ib-IX-V receptor on platelets. In healthy individuals, ULvWF multimers are immediately cleaved into smaller, regular-sized multimers by the vWF-cleaving protease ADAMTS13. This prevents ULvWF interaction with platelets and limits microthrombus formation. When there is severe ADAMTS13 deficiency, ULvWF released from the endothelium are not cleaved appropriately, leading to vWF-dependent platelet aggregation eventually resulting in microvascular thrombosis (9). The consumption of platelets in these microthrombi results in thrombocytopenia, one of the clinical feature of iTTP, and may present with muco-cutaneous bleeding symptoms such as epistaxis, bruising, petechiae, hematuria, and gastrointestinal bleeding (10, 11).

Prior to the availability of caplacizumab, episodes of iTTP were associated with an acute mortality of 10–20% and thromboembolic morbidities such as myocardial infarction and cerebrovascular accident. In addition, tissue ischemia caused by microvascular thrombosis may result in multiorgan dysfunction including renal dysfunction. Most patients have very high levels of lactate dehydrogenase (LDH) as a result of the combination of hemolysis and tissue ischemia. Elevations of serum troponin I and troponin T are common (12, 13).

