9.2.6.2 Clinical safety laboratory variables, vital signs and electrocardiograms (ECGs)

Clinical safety laboratory variables, vital signs and electrocardiogram (ECG) variables will be analyzed in the Safety population.

[figure not shown]
For clinical safety laboratory variables and vital signs, descriptive statistics for results and changes from baseline will be provided by time point during the on-treatment period. Clinical safety laboratory variables and vital signs will be converted into standard international units.

For ECG, the incidence of participants with at least one abnormal ECG during the treatment-emergent period will be summarized regardless of the baseline level and according to the following baseline status categories:

- Normal/missing
- Abnormal

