3 STATISTICAL ANALYSES

3.1 GENERAL CONSIDERATIONS

In general, continuous data will be summarized using the number of observations available, mean, standard deviation (SD), median, interquartile range (Q1, Q3), minimum, and maximum.

Categorical and ordinal data will be summarized using the count and percentage of participants.

No pre-specified success criterion or formal statistical hypothesis testing is planned. No statistical adjustment on interim analyses is planned.

When the notion of IMP is mentioned in the SAP, this refers to the study IMP.

The baseline value is defined as the last available value before the first dose of IMP, including participants who have received a dose of marketed caplacizumab for the presenting episode of iTP within 4 hours prior to enrollment. For participants enrolled but not treated with IMP, the baseline value is defined as the last available value before enrollment.

Efficacy endpoints derived from laboratory data (platelet count, lactate dehydrogenase [LDH], cardiac troponin I [cTnI], creatinine, ADAMTS13 activity) will be analyzed using central measurements, unless they are missing for a visit but the local value available, in which case the local value will be used under certain conditions (see [Section 5.4](#)). A central measurement will be considered missing if the recorded status is “NOT DONE” and there is a reason for this status or if status is “NOT PERFORMED”.

The observation period will be divided into 4 segments:

- The **pre-treatment period** is defined as the period up to the first caplacizumab administration (whatever marketed or study IMP).
- The **treatment-emergent (TE) period** is defined as the period from the first caplacizumab administration (whatever marketed or study IMP) up to the last caplacizumab administration **+ 28 days**. The TE period includes the following 2 periods:
 - The **on-treatment period** is defined as the period from the caplacizumab administration (whatever marketed or study IMP) to the last administration of caplacizumab.
 - The **residual treatment period** is defined as the period from the end of the on-treatment period to the end of the TE period.
- The **post TE period** is defined as the period from the end of the TE period.

The **overall study period** is defined as the time from the first caplacizumab administration (whatever marketed or study IMP) until the end of the study.

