Potentially clinically significant abnormality (PCSA) analyses will be performed based on the PCSA list currently in effect at Sanofi at the time of the database lock. For parameters for which no PCSA criteria are defined, similar analyses will be done using the normal range.

For laboratory parameters, local laboratory normal ranges (LLN, ULN) will be used with the local assessments, and central normal ranges with the central laboratory assessments.

Analyses according to PCSA will be performed based on the worst value, from the first study IMP to last IMP + 28 days, using all measurements (either local or central, either scheduled, non-scheduled or repeated).

[figure not shown]
For laboratory variables and vital signs variables above, the incidence of participants with at least one PCSA, will be summarized regardless of the baseline level and according to the following baseline status categories:

[figure not shown]
- Normal/missing
- Abnormal according to PCSA criterion or criteria

[figure not shown]
For ECG, the incidence of participants with at least one abnormal ECG, from the first study IMP to last IMP + 28 days, will be summarized regardless of the baseline level and according to the following baseline status categories:

- Normal/missing
- Abnormal

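### SAP 5.4 leaves in-hospital troponin, creatinine and LDH values out of the by-visit safety tables, and for pre-dosed participants the SAP uses two different start points

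*SAP*

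**What the plan says.** **By-visit tables.** SAP 3.6.3.1 lists creatinine, cTnI and LDH among the variables summarized, with change from baseline, by scheduled timepoint. SAP 5.4 (Additional assessments and hospitalization visits) then says: "All additional assessments and hospitalization visit measurements of laboratory data, vital signs and ECG will not be included in by-visit analyses". The sentence after it keeps those values for the abnormality counts: "PCSA analyses include all scheduled or unscheduled or additional visits assessments". Protocol 9.2.6.2 has no hospital exception: "descriptive statistics for results and changes from baseline will be provided by time point during the on-treatment period". Protocol 8.2.4 refers to Appendix 2 for the list of safety laboratory tests, and that list contains all three markers.

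**Sampling.** Protocol 1.3.2 is the hospital schedule: Days 1, 2 and 3, then daily from Day 4. Footnotes l and m to protocol 1.3.4, and note f to Table 8, require central LDH, cTnI and creatinine at baseline, 24, 48 and 60 hours and then daily in hospital. Weekly visits (protocol 1.3.3) start on Day 8.

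**Pre-dosed participants.** In SAP 3.1 the treatment-emergent period "is defined as the period from the first caplacizumab administration (whatever marketed or study IMP) up to the last caplacizumab administration", plus 28 days. The same section says that IMP means the study product only, and sets baseline as "the last available value before the first dose of IMP, including participants who have received a dose of marketed caplacizumab". In SAP 3.6.3.1 the PCSA analysis takes the worst value "from the first study IMP to last IMP + 28 days, using all measurements", and the abnormal-ECG count has the same window.

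**The concern.** The new element in this trial is going without plasma exchange at the start. Protocol 4.1 names rising troponin and worsening creatinine among the signs of organ injury that may lead to plasma exchange, including in the first 24 hours. Protocol 2.3.2 cites a case series in which platelets normalized after 48 to 96 hours. A safety table that has a gap from Day 4 to Day 7, or that begins at Day 8, cannot show how these markers moved in the period of most interest.

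An incidence count is a weak substitute when many participants may start with abnormal values. The protocol says of this disease: "Elevations of serum troponin I and troponin T are common". Exclusion criterion E 09 sets its numerical troponin limit at more than 5 x ULN, so participants can enter with raised values.

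For pre-dosed participants, change from baseline would be measured from a value taken after the first drug dose, although adverse events from that dose onward already count as treatment-emergent.

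**Working it through.** The plan gives no figure on this point to reproduce. The check is a count of draws, a comparison of outputs, and a measure of the pre-dosed gap.

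**1. Draws affected.** The post-baseline central draws before nominal Day 8 are 24 h (Day 2), 48 h and 60 h (Day 3), then one per hospital day from Day 4. If the last hospital draw is on Day d (4 to 7):

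- total draws = 3 + (d − 3) = d
- omitted, narrow reading (Days 2 and 3 kept as scheduled visits) = d − 3
- omitted, broadest reading (everything in the hospital schedule) = d

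| Last hospital draw | Narrow reading | Broadest reading |
|---|---|---|
| Day 4 | 1 of 4 | 4 of 4 |
| Day 5 | 2 of 5 | 5 of 5 |
| Day 6 | 3 of 6 | 6 of 6 |
| Day 7 | 4 of 7 | 7 of 7 |

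Length of stay is not given; protocol 4.1 says that it varies. The weekly visit has a window of ±3 days, so the first one could fall anywhere from Day 5 to Day 11.

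**2. What the other visible outputs show.**

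- *PCSA counts* use in-hospital values, but report only whether a participant had at least one abnormality, by normal/missing or abnormal baseline. The sponsor's PCSA list is not in the documents. If it has no troponin criterion (an assumption), SAP 3.6.3.1 falls back on the normal range. A participant stable at 2 x ULN and one rising from 2 x to 20 x ULN would then be counted alike.
- *The TTP event form* records onset, severity, outcome and the troponin value (protocol 8.1.2), but for neurological and cardiac findings only once the investigator judges the abnormality a clinically significant event (8.1.3, 8.1.4).
- *Adverse events* include disease-related laboratory findings only if they are judged more severe than expected (protocol 8.2.4, 10.3.1).
- *Graphs* in SAP 5.4 cover platelets, LDH and ADAMTS13 activity from Day 4. LDH is therefore partly covered; cTnI and creatinine are not named.
- *Time-to-event outputs* for cTnI and creatinine measure return to normal, not worsening. The cTnI formula is also written in terms of creatine, which looks like a copying slip.

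**3. The pre-dosed gap.**

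- Marketed dose to first study dose: 4 to 6 h (protocol 1.3.2 footnote o, 1.3.4 footnote c).
- Share of the first 24 h: 4/24 = 17% to 6/24 = 25%.
- Longest possible window: (84 + 28) × 24 = 2,688 h, so the gap is at most 6/2,688 = 0.2% of it.
- Central draws in the gap: sampling time 0 is enrollment, which is at most 4 h after the marketed dose. The time-0 draw is therefore post-drug and can become the baseline. The next central draw, at 24 h, is inside the PCSA window. Normally one central cTnI and creatinine draw is affected.

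**The case against.** A reader might infer that early organ damage is hidden. The documents do not support that. In-hospital worst values enter the PCSA counts, TTP events are assessed daily in hospital and feed the clinical response definition, and the reason for and timing of plasma exchange are summarized (SAP 5.3).

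A reader might also take it as settled that the by-visit tables start at Day 8. That is only the broadest reading. Day 1 belongs to the same hospital schedule, so that reading would also remove the Day 1 values on which change from baseline depends. SAP 5.4 separately says that by-visit safety analyses use scheduled visits, and its Table 7 lists Days 2 and 3 as scheduled, though only for patient-reported and pharmacodynamic data. The narrow reading is more plausible. It still loses Days 4 to 7.

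A third tempting inference is that the SAP's ECG window contradicts the protocol. It does not: protocol 9.2.1 starts the treatment-emergent period at the first IMP dose, and the SAP baseline follows the protocol too. The inconsistency is within the SAP, which moved the start of its treatment-emergent period but not these rules. Nor does the exclusion cost anything for ECGs, since neither document plans by-visit ECG statistics. For vital signs the hospital schedule has a Day 1 entry only.

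Redaction is a fair limit. The exploratory endpoints are blacked out, and a by-day marker summary may exist there. That would supply the missing information, but it would not reconcile SAP 5.4 with protocol 9.2.6.2.

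**Conclusion.** The point holds in this limited form. SAP 5.4 states an exclusion with an undefined term, and following it departs from protocol 9.2.6.2. The loss is 4 of 7 scheduled central draws before Day 8 on the narrow reading, and up to 7 of 7 on the broadest, assuming a stay through Day 7; shorter stays lose fewer. Early worsening is captured, but for cTnI and creatinine its size and time course appear in no visible output. For LDH there is a graph from Day 4.

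The pre-dosed inconsistency is real but smaller: 4 to 6 hours, normally one central draw, in a subgroup whose size the documents do not give. It cannot conceal worsening over the first days.

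Neither point affects the sample size, the primary estimate or its confidence interval. Both merit a SAP amendment because the data are already being collected.

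**What to change.** **SAP 5.4:** limit the exclusion to unscheduled assessments and re-hospitalizations. Tabulate the scheduled in-hospital cTnI, creatinine and LDH values by day to Day 7, with n and change from baseline. SAP 5.4 already derives one value per day for these markers for efficacy, so little new programming is needed.

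**SAP 3.6.3.1:** start the PCSA and ECG windows at the first caplacizumab dose, marketed or study, to match the SAP's treatment-emergent period.

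**SAP 3.1:** for pre-dosed participants, take as safety baseline the last value before the first caplacizumab dose where one exists on the same analyte and assay. Otherwise flag the baseline as post-dose.

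**Cost:** SAP wording and a few table columns. Denominators will shrink from Day 4 as participants go home, so n must be shown at each day. Some pre-dosed participants will have only a local pre-drug value, or one from a different troponin assay, since screening allows cTnT and high-sensitivity tests; those should not be mixed with later central cTnI. The new window and baseline also differ from protocol 9.2.1, so the SAP's record of changes should say so.
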